9.4.2 Glucodynamic Statistical Inference

The GD statistical model will be the same as the model used for the analysis of the PK parameters. The following variables will be log-transformed prior to analysis: R_{max} , G_{tot} , $G_{tot}(0-30min)$, and $G_{tot}(0-1h)$. Additional partial glucose AUCs, such as $G_{tot}(0-2h)$ and $G_{tot}(3-10h)$, may be analyzed as necessary. For GD parameters that have at least 1 patient with a value equal to zero, an analysis of original scale data (not log-transformed) will be performed as described below for the GD time parameters.

The same model without log transformation will be used for the analysis of the GD time parameters (T_{onset} , TR_{max} , early 50% TR_{max} , and late 50% TR_{max}). Least-squares means, treatment differences in least-squares means, and the corresponding 95% CIs for the treatment differences will be estimated from the model. The p-value for the difference between least-squares means will be used to determine statistical significance. The treatment ratios and 95% CIs for the ratios will be calculated using Fieller's theorem.

The analyses described above will also be performed on the population of patients who complete and have evaluable GD data for both study periods.

9.5 Safety and Tolerability Assessments

9.5.1 Adverse events

Where changes in severity are recorded in the Case Report Form (CRF), each separate severity of the adverse event (AE) will be reported in the listings, only the most severe will be used in the summary tables. A pre-existing condition is defined as an AE that starts before the patient has provided written informed consent and is ongoing at consent. A non-treatment emergent AE is

defined as an AE which starts after informed consent but prior to the first dose. A treatment-emergent AE is defined as an AE which occurs postdose or which is present prior to dosing and becomes more severe postdose.

All AEs will be listed. Treatment-emergent AEs will be summarized by treatment, severity and relationship to the study drug. The frequency (the number of AEs, the number of patients experiencing an AE and the percentage of patients experiencing an AE) of treatment-emergent AEs will be summarized by treatment, Medical Dictionary for Regulatory Activities (MedDRA) version 20.0 system organ class and preferred term. The summary and frequency AE tables will be presented for all causalities and those considered related to the study drug. Any serious AEs will be tabulated.

9.5.2 Blood Glucose Monitoring and Hypoglycemia

Hypoglycemic events will be appropriately recorded in the CRF. In the case of a hypoglycemic event, the actual blood glucose value, if measured, will be recorded in the CRF, together with any treatments administered. Each category of hypoglycemic events (defined below) will be listed and summarized by treatment.

Hypoglycemia is defined as follows:

- **Documented Glucose Alert Level (Level 1), Plasma Glucose (PG) ≤ 70 mg/dL (3.9 mmol/L):**
 - **Symptomatic hypoglycemia:** an event during which typical symptoms of hypoglycemia are accompanied by PG ≤ 70 mg/dL (3.9 mmol/L)
 - **Asymptomatic hypoglycemia:** an event not accompanied by typical symptoms of hypoglycemia but with PG ≤ 70 mg/dL (3.9 mmol/L)
 - **Unspecified hypoglycemia:** an event during which PG ≤ 70 mg/dL (3.9 mmol/L) but no information relative to symptoms of hypoglycemia was recorded
- **Documented Clinically Significant Hypoglycemia (Level 2) PG < 54 mg/dL (3.0 mmol/L):**
 - **Symptomatic hypoglycemia:** an event during which typical symptoms of hypoglycemia are accompanied by PG < 54 mg/dL (3.0 mmol/L)
 - **Asymptomatic hypoglycemia:** an event not accompanied by typical symptoms of hypoglycemia but with PG < 54 mg/dL (3.0 mmol/L)
 - **Unspecified hypoglycemia:** an event during which PG < 54 mg/dL (3.0 mmol/L) but no information relative to symptoms of hypoglycemia was recorded
- **Severe hypoglycemia (Level 3):** an event requiring assistance of another person to actively administer carbohydrate, glucagon, or other resuscitative actions. During these episodes, the patient has an altered mental status and cannot assist in their care, is

semiconscious or unconscious, or experienced coma with or without seizures and may require parenteral therapy. PG measurements may not be available during such an event, but neurological recovery attributable to the restoration of blood glucose concentration to normal is considered sufficient evidence that the event was induced by a low PG concentration (PG \leq 70 mg/dL [3.9 mmol/L])

Other Hypoglycemia:

- **Nocturnal hypoglycemia:** any hypoglycemic event (documented symptomatic, asymptomatic, probable symptomatic, or severe hypoglycaemia) that occurs between bedtime and waking
- **Relative hypoglycemia:** an event during which typical symptoms of hypoglycemia, which do not require the assistance of another person, are accompanied by PG $>$ 70 mg/dL (3.9 mmol/L), but these levels may be quickly approaching the 70 mg/dL (3.9 mmol/L) threshold
- **Overall (or total) hypoglycemia:** This optional category combines all cases of hypoglycemia. If an event of hypoglycemia falls into multiple subcategories, the event is counted only once in this category
- **Probable symptomatic hypoglycemia:** An event during which symptoms of hypoglycemia are not accompanied by a PG measurement but that was presumably caused by a blood glucose concentration \leq 70 mg/dL (3.9 mmol/L).

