9.4.7.2. Glucose Monitoring

Hypoglycemia will be described using the following definitions:

Documented Glucose Alert Level (Level 1)

Plasma glucose ≤ 70 mg/dL (3.9 mmol/L)

- *Documented symptomatic hypoglycemia:* with typical symptoms of hypoglycemia.
- *Documented asymptomatic hypoglycemia:* without typical symptoms of hypoglycemia.
- *Documented unspecified hypoglycemia:* with no information about symptoms of hypoglycemia available. (This has also been called unclassifiable hypoglycemia.)

Documented Clinically Significant Hypoglycemia (Level 2)

Similar criterion as for Level 1, except for threshold PG < 54 mg/dL (3.0 mmol/L)

- *Level 2 documented symptomatic hypoglycemia*
- *Level 2 documented asymptomatic hypoglycemia*
- *Level 2 documented unspecified hypoglycemia*

Severe Hypoglycemia (Level 3)

Patient had altered mental status and could not assist in their own care, was semiconscious or unconscious, or experienced coma with or without seizures, and the assistance of another person was to actively administer carbohydrate, glucagon, or other resuscitative actions. Plasma glucose measurements may not be available during such an event, but neurological recovery attributable to the restoration of PG concentration to normal is considered sufficient evidence that the event was induced by a low PG concentration (PG \leq 70 mg/dL [3.9 mmol/L]).

Other Hypoglycemia

- *Nocturnal hypoglycemia*: Any documented hypoglycemic event (including severe hypoglycemia) that occurs at night and presumably during sleep. This is captured as hypoglycemia that occurs between bedtime and waking. This definition is more useful than the commonly used approximately 00:00 to 06:00 definition which does not take patients' individual sleep times into consideration, and is consistent with the American Diabetes Association recommendations of reporting events that occur during sleep (ADA 2005). It is also important to collect the actual time when a hypoglycemic event occurred to allow further characterization of hypoglycemia timing (eg, to allow analysis of frequency of events occurring across a 24-hour clock). Nocturnal hypoglycemia may occur at severity Levels 1, 2, or 3.

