- *Relative hypoglycemia (also referred to as pseudohypoglycemia [Seaquist et al. 2013])*: An event during which typical symptoms of hypoglycemia occur, that does not require the assistance of another person and is accompanied by PG $>$ 70 mg/dL (3.9 mmol/L). The PG value of patients with chronically poor glycemic control can decrease so rapidly that patients may report symptoms of hypoglycemia before their PG concentration falls below 70 mg/dL (3.9 mmol/L). Events with PG \leq 70 mg/dL should not be categorized as relative hypoglycemia. Evaluation and statistical analysis of this category is optional. However, if a patient reports a relative hypoglycemia event where assistance from another person was received or the patient experienced significant symptoms, the study team should clarify the circumstances to ensure the event is not a severe hypoglycemia event, and report it appropriately.
- *Probable symptomatic hypoglycemia*: Symptoms of hypoglycemia were present, but PG measurement was not reported.
- *Overall (or total) hypoglycemia*: This optional category combines most cases of hypoglycemia (documented hypoglycemia and probable symptomatic hypoglycemia, including severe hypoglycemia). It does not include relative hypoglycemia. Nocturnal and severe hypoglycemia are special cases of documented or probable hypoglycemia. If an event of hypoglycemia falls into multiple subcategories, that event should only be counted once in the category of overall (or total) hypoglycemia.

Only severe hypoglycemic episodes will be reported separately as AEs. All episodes of severe hypoglycemia will be reported as SAEs.

The goal of the euglycemic clamp is to maintain blood glucose concentrations at euglycemic levels close to a predefined target. Therefore, glucose concentrations below 70 mg/dL will not routinely be recorded as hypoglycemic events during the glucose clamp procedure. However, at the discretion of the investigator, a decrease in glucose concentration may be recorded as a hypoglycemic event based on clinical concern or related to technical issues resulting in hypoglycemia.

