11. CHANGES FROM THE PROTOCOL SPECIFIED STATISTICAL ANALYSES

There were no changes from the protocol specified statistical analyses.

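### The SAP's nocturnal hypoglycemia list leaves out documented events of unspecified symptom status, and it includes probable symptomatic events, on which the protocol contradicts itself

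*SAP*

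**What the plan says.** Protocol 9.4.7.2 (Glucose Monitoring) defines the nocturnal category as "Any documented hypoglycemic event (including severe hypoglycemia) that occurs at night and presumably during sleep" and adds that "Nocturnal hypoglycemia may occur at severity Levels 1, 2, or 3". The same section divides documented events, at Level 1 and again at Level 2, into symptomatic, asymptomatic and unspecified. The last group consists of events "with no information about symptoms of hypoglycemia available". Probable symptomatic hypoglycemia is a separate category: "Symptoms of hypoglycemia were present, but PG measurement was not reported". Further on, under overall hypoglycemia, the protocol describes nocturnal events, like severe ones, as subsets of either documented or probable hypoglycemia.

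SAP 9.5.2 uses the same three documented subtypes at both levels. Its unspecified subtype requires PG at or below 70 mg/dL (Level 1) or below 54 mg/dL (Level 2), "but no information relative to symptoms of hypoglycemia was recorded". Its nocturnal category is "any hypoglycemic event (documented symptomatic, asymptomatic, probable symptomatic, or severe hypoglycaemia) that occurs between bedtime and waking". It defines probable symptomatic as "An event during which symptoms of hypoglycemia are not accompanied by a PG measurement". The section says that every hypoglycemia category will be tabulated for each treatment as well as listed.

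SAP Section 3 says that the SAP takes precedence over the protocol's statistical considerations and that substantial differences will be pointed out. SAP Section 11 reads: "There were no changes from the protocol specified statistical analyses".

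**The concern.** The nocturnal definition drives a row in a reported safety summary. Of the three documented subtypes, only unspecified is missing from the SAP's list, and nothing in either document explains why. A programmer building the flag from the listed types would leave out a night-time event with a confirmed low PG because nobody recorded whether the patient had symptoms. That combination is plausible at night, when a patient may be asleep. The same flag would count an event with symptoms and no glucose value.

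Safety and tolerability is a secondary objective, and hypoglycemia is the first potential risk that the protocol names. Only severe episodes are reported as adverse events, so non-severe night-time events are summarized through these categories and not through the adverse event tables. A reader of the study report would assume that the nocturnal row follows the protocol's definition and would have nothing to say otherwise.

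**Working it through.** There is no stated nocturnal count or rate to reproduce. The check is which event types each text admits. All rows refer to events that occur overnight.

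| Event type | PG value | Protocol 9.4.7.2, nocturnal definition | Protocol 9.4.7.2, sentence under overall hypoglycemia | SAP 9.5.2 list |
|---|---|---|---|---|
| Documented symptomatic | yes | in | in | in |
| Documented asymptomatic | yes | in | in | in |
| Documented unspecified | yes | in | in | **not listed** |
| Severe | may be absent | in | in | in |
| Probable symptomatic | none | **out** | **in** | in |
| Relative | above 70 mg/dL | out | out | not listed |

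Step 1, the omission. Both protocol statements admit unspecified events because they are documented events. The SAP list does not. This difference holds under either protocol statement.

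Step 2, the addition. Probable symptomatic events fall outside the protocol's nocturnal definition, which asks for documented or severe events, but inside its later sentence. The SAP agrees with one protocol statement and not the other.

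Step 3, the effect on the count. Let S, A, U, V and P be the night-time counts of documented symptomatic, documented asymptomatic, documented unspecified, severe and probable symptomatic events, each event counted once.

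- SAP row: S + A + V + P
- Protocol, narrow reading (documented or severe): S + A + U + V
- Protocol, wide reading (documented, severe or probable): S + A + U + V + P
- SAP minus narrow: P − U
- SAP minus wide: −U

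Under the wide reading the SAP row is short by exactly U. Under the narrow reading the two differences can offset each other, so the totals may agree while the events behind them differ. If U = 0 and P = 0, all three counts are the same.

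Step 4, an illustration with assumed counts, since the documents give none. Take S + A + V = 7, U = 3 and P = 2. The SAP row shows 7 + 2 = 9. The narrow reading gives 7 + 3 = 10, and the wide reading gives 7 + 3 + 2 = 12. Of the SAP's 9 events, 7 qualify under the narrow reading and all 9 under the wide one. The 3 unspecified events are missing in either case.

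**The case against.** The strongest reply is that the protocol itself lets probable events be nocturnal, so the SAP cannot be faulted for including them. That stands. A reader might infer that the SAP row is wrong in both directions, but the documents do not support this. Only the omission is an unambiguous difference. A missing glucose value is not disqualifying in itself either, because severe events without one already qualify.

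A reader might also infer that the protocol requires nocturnal events to be tabulated by level. It says only that they can occur at each level; it specifies no such table.

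Nor are the omitted events lost to the report. The SAP tabulates the unspecified categories at Levels 1 and 2 and lists all data held in the database. The gap is in the nocturnal row alone.

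It can be said that the opening words of the SAP definition are broad and the parenthesis merely illustrative. This is weaker: nothing marks the list as a set of examples, and it reads as complete.

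SAP Section 11 refers to statistical analyses, while the nocturnal definition sits in the protocol's safety monitoring section. The no-change statement is therefore not plainly false on this point. What remains is that the SAP nowhere tells the reader that its list differs.

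Finally, the consequence is small. Each patient receives two single doses of an insulin whose half-life the protocol gives as about 0.92 hours, and washout nights are spent largely on the patient's own regimen. Nocturnal counts will say little about the treatment comparison. This stands, and it limits the importance of the point without removing the mismatch.

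**Conclusion.** The omission of documented unspecified events from the SAP's nocturnal definition is a real mismatch with the protocol, and with the SAP's own subtypes. On probable symptomatic events the fault lies first in the protocol, which says two different things; the SAP follows one of them without comment.

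The size is modest. The nocturnal row would be short by the number of unspecified night-time events, and would also contain any probable symptomatic events, whose place is unsettled. Neither document gives a rate, so the shortfall cannot be estimated; it is zero if no such event occurs. It would be too strong to say that the counts will be wrong; they may be. The effect stays within one descriptive safety summary. Severe events are in every version of the definition, so the AE endpoint is unaffected, and no PK or GD analysis uses this category.

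The conclusion assumes that the SAP's list is programmed as written. It is worth correcting because the correction is cheap and makes a reported safety count match its definition.

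**What to change.** 1. In SAP 9.5.2, extend the nocturnal definition to all documented events at Levels 1 and 2, whether symptomatic, asymptomatic or unspecified, together with severe events.
2. Reconcile the two statements in Protocol 9.4.7.2 on whether probable symptomatic events can be nocturnal. If they are kept, show them on a separate line within the nocturnal summary, so that events with and without a glucose value can be told apart.
3. State any remaining difference from the protocol's definition in SAP Section 11.

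A breakdown of nocturnal events by level would be useful but is optional.

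The SAP change costs one sentence and one derivation flag, plus a table line if probable symptomatic events are shown separately. Settling the protocol inconsistency takes a short clarification. No new data are needed.

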3. INTRODUCTION

This SAP has been developed after review of the Clinical Study Protocol (final version dated 07 November 2017), the version 1 SAP (final version 1 dated 12 January 2018) and the version 2 SAP (final version 2 dated 27 April 2018).

This SAP describes the planned analysis of the safety, tolerability, pharmacokinetic (PK) and pharmacodynamic (PD) data from this study. A detailed description of the planned TFLs to be presented in the clinical study report (CSR) is provided in the accompanying TFL shell document.

The intent of this document is to provide guidance for the statistical, PD and PK analyses of data. In general, the analyses are based on information from the protocol, unless they have been modified by agreement between Eli Lilly and Company and CCI. A limited amount of information concerning this study (e.g., objectives, study design) is given to help the reader's interpretation. This SAP must be signed off prior to first patient administration for this study. When the SAP and TFL shells are agreed upon and finalized, they will serve as the template for this study's CSR.

This SAP supersedes the statistical considerations identified in the protocol; where considerations are substantially different, they will be so identified. If additional analyses are required to supplement the planned analyses described in this SAP, they may be performed and will be identified in the CSR. Any substantial deviations from this SAP will be agreed upon between Eli Lilly and Company and CCI and identified in the CSR. Any minor deviations from the TFLs may not be documented in the CSR.

This SAP is written with consideration of the recommendations outlined in the International Council on Harmonisation (ICH) E9 Guideline entitled Guidance for Industry: Statistical Principles for Clinical Trials¹ and the ICH E3 Guideline entitled Guidance for Industry: Structure and Content of Clinical Study Reports².

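### SAP 9.5.2 defines overall hypoglycemia as all cases and drops the protocol's exclusion of relative hypoglycemia, without declaring the change

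*SAP*

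**What the plan says.** Both documents define a category called overall (or total) hypoglycemia, and both say that an event falling into several subcategories is counted once. They differ on what goes in.

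- Protocol Section 9.4.7.2: "This optional category combines most cases of hypoglycemia (documented hypoglycemia and probable symptomatic hypoglycemia, including severe hypoglycemia). It does not include relative hypoglycemia". Of relative hypoglycemia itself, the protocol says: "Evaluation and statistical analysis of this category is optional".
- SAP Section 9.5.2, on the overall category: "This optional category combines all cases of hypoglycemia". No components are named and no exclusion is given.
- SAP Section 9.5.2, on relative hypoglycemia: "an event during which typical symptoms of hypoglycemia, which do not require the assistance of another person, are accompanied by PG" above 70 mg/dL (3.9 mmol/L). This is one of the entries under Other Hypoglycemia, within the section's list of hypoglycemia definitions.
- SAP Section 9.5.2, on reporting: "Each category of hypoglycemic events (defined below) will be listed and summarized by treatment".
- SAP Section 3, on precedence: "This SAP supersedes the statistical considerations identified in the protocol; where considerations are substantially different, they will be so identified".
- SAP Section 11: "There were no changes from the protocol specified statistical analyses".

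**The concern.** One named category has two definitions. A programmer working from the SAP, which takes precedence over the protocol, could count symptomatic events with PG above 70 mg/dL in the overall total. A reader of the study report who relies on SAP Section 11 would assume that the protocol's exclusion still applied. The same table would then be built under one rule and read under another.

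Safety and tolerability is a secondary objective, and hypoglycemia is the first potential risk that protocol Section 3.3 names. The protocol also says that glucose values below 70 mg/dL during the clamp will not routinely be recorded as hypoglycemic events, so the recorded count may be small. In a crossover planned for about 28 completers, a few relative events could then visibly change a by-treatment total.

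**Working it through.** The plan states no figure for this category, so there is none to reproduce. The check is a comparison of definitions, followed by a counting identity.

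**Step 1. Components of the total.**

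| Event type | Protocol 9.4.7.2 total | SAP 9.5.2 total, read literally |
|---|---|---|
| Documented, Level 1 or Level 2 (symptomatic, asymptomatic, unspecified) | in | in |
| Probable symptomatic (no PG value) | in | in |
| Severe, Level 3 | in | in |
| Relative (symptoms, PG above 70 mg/dL, no assistance needed) | out, expressly | in, because it is a listed category and nothing excludes it |

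Nocturnal hypoglycemia is a timing label on other events and adds no separate type to either total.

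**Step 2. Overlap.** Under the SAP's own definitions, a relative event cannot also belong to another component:

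- Levels 1 and 2 need PG at or below 70 mg/dL and below 54 mg/dL respectively; a relative event has PG above 70 mg/dL.
- A probable symptomatic event has no PG measurement; a relative event has one.
- A severe event needs another person's help; a relative event does not.
- The SAP's nocturnal definition names its qualifying types, and relative is not among them.

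The count-once rule therefore removes no relative event from the SAP total.

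**Step 3. Identity for event counts.** Let P be the protocol total and R the number of relative events in a treatment arm. Then

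SAP total = P + R.

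If R = 0 the totals agree. If R is 1 or more, the SAP total is higher by exactly R.

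**Step 4. Patients rather than events.** The SAP does not say whether the hypoglycemia summary counts events, patients or both. For patients with at least one event, the excess is the number of patients whose only events were relative. That lies between 0 and R.

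**Step 5. Relative size.** The proportional excess is R / P, and the documents give neither term. Suppose a fraction f of S symptomatic events with a PG value is relative, and there are A events of other kinds. The excess is then fS / [(1 − f)S + A]. Taking f from 0.10 to 0.20 purely as an assumption:

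- A = 0: 0.10/0.90 = 11% to 0.20/0.80 = 25%.
- A = S: 0.10/1.90 = 5% to 0.20/1.80 = 11%.

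The result is driven by f and A, neither of which is in the documents. Only the absolute statement in Step 3 can be made from them.

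**The case against.** **Inclusion is inferred, not stated.** No SAP sentence says that relative events enter the total. The SAP's nocturnal definition spells out what it means by any hypoglycemic event, and that list omits relative events. One could therefore read all cases in the overall definition as carrying the same limit. This shows that the wording can be read two ways, but it does not remove the problem. The nocturnal entry shows that the SAP names the qualifying types when it wants a restricted set, and the overall entry names none. The protocol's components and exclusion sentence are both absent, and relative hypoglycemia is listed among the definitions. Inclusion is the plain reading, though it remains an implication.

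**The category is optional.** Both documents say so, and if the total is never produced, nothing follows. This stands as a condition on the point. It does not settle the matter, because the SAP also promises a summary of each defined category, and an optional total still needs a single definition.

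**The effect can be undone.** If relative hypoglycemia is summarized as its own category, as the SAP promises, subtracting it from the event total gives the protocol figure. This stands for event counts. For patient counts the correction needs the individual listings, which the SAP also promises.

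**Section 11 may not have been obliged to mention it.** Section 11 concerns protocol-specified statistical analyses. The protocol's safety analysis sections (10.3.1 onward) specify no hypoglycemia analysis; the definition sits under safety monitoring. SAP Section 3 promises to flag only substantial differences. This has force, so the absence of a declaration is better seen as leaving the discrepancy unsignalled than as a breach of the SAP's own rule.

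**Conclusion.** The two definitions conflict, and the SAP's rule, followed literally, departs from the protocol. The event total exceeds the protocol's by the number of relative events, on two conditions: the overall category is reported, and at least one relative event is recorded. The conclusion rests on reading all cases to mean every category that SAP 9.5.2 lists.

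The point is minor. It affects a descriptive safety summary, and SAP 9.5.12 plans no inferential safety analysis. The primary pharmacokinetic endpoints, the glucodynamic endpoints, the power figures and the reporting of severe hypoglycemia as serious adverse events are untouched.

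A reader might infer more, and the documents do not support it:

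- *That the reported total will be wrong.* This depends on the two conditions above.
- *That this is the headline hypoglycemia figure.* Neither document gives it that status. The listed safety endpoint is adverse events, and only severe episodes are reported separately as adverse events.
- *That the total would not be comparable with other studies.* The documents do not show what definition other studies use.
- *That the overstatement can be given as a percentage.* No rate of relative events is stated, and the illustration above runs from 5% to 25% on assumptions alone.

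**What to change.** In SAP 9.5.2, restore the protocol's definition: overall hypoglycemia comprises documented, probable symptomatic and severe events, each counted once, and excludes relative hypoglycemia, which is shown separately. If the broader definition is intended, declare and justify it in SAP Section 11.

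In the same edit, reconcile the word optional with the promise to summarize every category, by stating whether the overall category will be reported. It would also help to say whether the summary counts events, patients or both.

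The cost is one or two sentences in the SAP and a matching check of the table shells. No data collection, sample size or endpoint changes.
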